Participants will also engage in the trauma-imagery procedure, followed by participation in the Taylor Reaction Time Task (TRT; Taylor, 1967). For this part of the post-treatment session, participants will be seated in one of two humidity and temperature controlled sound-proof booths located in the biological studies laboratory at the WHVA. Participants will be seated in front of a monitor and keyboard connected to a computer located outside of the booths. An intercom will be placed next to the keyboard for participants to use to communicate with the experimenter during the tasks. After orientation to the subject room, electrodes will be attached and the subject will be instructed to sit quietly for 5 minutes to assess baseline recordings. Next, participants will listen to the 60-second audio recording of the script depicting their traumatic event. They will be instructed to listen carefully during the playing of the script and to attempt to imagine as vividly as possible the experience as it is presented. After the script terminates, participants will be instructed to continue to imagine the experience from beginning to end (for 60 seconds) until they hear a tone. Participants will then be instructed to rest (for 5 minutes) until a second tone is heard and then they will then make several ratings of their subjective experiences while they were recalling the traumatic event. Next, they will complete the Taylor Reaction Time Task (TRT; Taylor, 1967) to assess provoked aggression.

Debriefing

At the end of the post-treatment session, once all of the procedures have been completed, the experimenter will conduct a verbal debriefing with participants during which they will clarify all aspects of the deception that occurred during the TRT so that there is no misinformation, assess any distress that the participants may have experienced, and make every effort to minimize this distress through the debriefing discussion.

Debriefing participants following completion of a research study is a standard component of research with human subjects and serves several especially important functions in studies involving deception. These include: 1) allowing the participant to provide fully informed consent for the use of their data in the study; 2) providing the participant the opportunity to express any

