To the extent that participants are experiencing any remaining distress as a result of their trauma exposure, the experimenter will work with the participant to assist them in returning to baseline levels of functioning. Finally, before ending the study appointment, participants will be informed that they will be contacted between 48-72 hours and then again one-week after their participation to follow-up about any negative reactions they may have had as a result of this portion of the session.

At the end of the post-treatment session, participants will be scheduled for a follow-up session to take place approximately 3 months after the post-treatment session to be held at the WHVA.

Follow-up Session. At this session, all participants will complete a similar assessment battery as was completed at the baseline and post-treatment sessions to assess any changes in levels of anger and aggression that may have occurred over the previous 3 months.

Drug and Alcohol Screening

At the beginning of the post-treatment session, participants will be asked to provide a urine sample to test for urine toxicology. If participants test positive on urine toxicology exams, we will encourage these individuals to maintain abstinence and they will be rescheduled. We will offer brochures for local substance use treatment facilities as appropriate. The extent to which participants are experiencing any symptoms of withdrawal will also be determined using the Clinical Institute Withdrawal Assessment for Alcohol Scale (CIWA-Ar; Sullivan et al., 1989). If participants indicate that they are experiencing any symptoms of withdrawal, they will be asked to reschedule their appointment at a later date. We will provide referrals to appropriate primary

care providers as appropriate.

Compensation

Participants will be compensated for their time and inconvenience while taking part in study procedures. Participants will be paid \$100 for the baseline and post-treatment sessions, and \$50 for the follow-up session. Participants also will be paid \$20 for completing questionnaires during week 3 and week 6 of treatment (for a total of \$40). Participants will not be paid for their participation in the TREC or MBSR intervention.

Assessments: See Table 1 for a listing of the primary assessments used in the current study.

Table 1. Schedule of Assessments

| | Baseline | 3-week | 6-week | Post-Treatment | 3-month Follow-up |
|--|----------|--------|--------|----------------|-------------------|

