- Five Facet Mindfulness Questionnaire (FFMQ; Baer et al., 2008)
- PTSD Checklist for the DSM-V (PCL-5; Weathers et al., 2013)
- Quantity-Frequency Variability Index (QFI; Cahalan, Cisin, & Crossley, 1969)
- Alcohol Dependency Scale (ADS; Skinner & Allen, 1982)

Interim Assessments: During the intervention period, at two time points (weeks 3 and 6 of therapy), participants will be asked to complete the STAXI-2, the BPAG, the FFMQ, the PCL-5, the QFI, and the ADS.

Post-treatment Session: Participants will complete the same battery of self-report questionnaires that was completed at the baseline session. In addition, participants also will complete the following assessments. (See Figure 3 below outlining the order of tasks during experimental portion of the post-treatment session.)

(c) Psychophysiological Assessments: During the experimental portion of the post-treatment session, physiological measurements will be recorded to assess reactivity during exposure to the trauma cue (script). Participants will sit quietly for 5 minutes to collect baseline (B) physiological assessments. This will be followed by the trauma-script reading (TR) and then the trauma-script imagery (TI) segments followed by a resting period (R) and assessment of subjective experiences.

Physiological measurements will include skin conductance levels (SC) and heart rate levels (HR). A BIOPAC MP150 system (BIOPAC, Santa Barbara, CA) that includes modules for HR and SC will be used to record physiologic analog signals. Physiologic analog signals will be digitized by an analog to digital converter. A notebook computer (IBM-compatible) with BIOPAC Acknowledge© software will be used to sample and store the digitized physiologic signals. Interbeat interval will be recorded in milliseconds via standard limb electrocardiogram leads connected to a High Gain Bioamplifier and converted to HR. Skin Conductance (SC) will be measured by an Isolated Skin Conductance coupler using a constant .5 V through 2, 9-mm (sensor diameter) Ag/AgCl electrodes filled with electroconductive gel placed on the hypothenar surface of the subject's non-dominant hand in accordance with published guidelines. The SC electrodes will be separated by 14 mm, as determined by the width of the adhesive collar.

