Figure 3. Order of tasks during the experimental portion of the post-treatment session

Follow-up Session. Participants will complete the same self-report questionnaires that were completed at the baseline and post-treatment sessions: STAXI-2, BPAQ, PCL-V, QFI, ADS, and the FFMQ.

Study Conditions:

Trauma Recovery Education Class (TREC). TREC is a group-based treatment that was developed by two staff clinicians at the WHVA. It is based in part on the first session of Cognitive Processing Therapy (Resick & Schnicke, 1993), which focuses on providing information on PTSD and traumatic reactions, and Motivational Enhancement Therapy (Miller & Rollnick, 2012). TREC provides psycho-education to veterans on PTSD, including common reactions to trauma and the role of avoidance, common problems associated with PTSD, as well as common barriers to care (e.g., stigma, maladaptive beliefs, fear). Additional content focuses on problem identification and goal setting, discussion of current problems and life issues, and treatment planning. The content of TREC is similar to other treatment control conditions used in RCTs with veterans with PTSD (e.g., Schnurr et al., 2001; Shea, Lambert, & Reddy, 2013). Such interventions emphasize therapist contact and support, as well as the provision of psychoeducation, instillation of hope and the expectation of improvement. The complete version of TREC will be implemented for the current project, which consists of 8, one-hour weekly sessions. TREC will be conducted by a doctoral level clinician (to be named) at the WHVA.

Mindfulness Based Stress Reduction (MBSR): MBSR, developed by Jon Kabat-Zinn (Kabat-Zinn, 1990) is a group-based intervention that was initially developed for individuals experiencing chronic pain and other stress-related disorders. Subsequent research has found it to be effective with individuals experiencing emotional distress including depression and anxiety (Baer, 2003). In MBSR, participants are taught different mindfulness meditation practices, including body scan (focusing attention to different areas of the body in sequence), sitting meditation (focusing attention to one’s breathing), and Hatha yoga postures (focusing attention

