to different body sensations during gentle stretching). Participants also are taught how to practice mindfulness while engaging in ordinary activities including walking, standing, and eating. When practicing mindfulness, participants are instructed to focus their attention on the target of observation (e.g., breathing or walking). If any emotions, sensations, or thoughts arise, participants are instructed to note that they have occurred (i.e., to observe them) and to do so in a non-judgmental manner. They are then instructed to re-focus their attention to the present moment. Doing so helps participants to notice their thoughts and feelings, but not be overwhelmed or absorbed by their content (Kabat-Zinn, 1982). MBSR consists of 8, two-hour weekly sessions and will be delivered in group format. The MBSR groups will be conducted by [name].

Treatment Adherence: To enhance treatment adherence, manuals will be used for both the TREC and MBSR groups. Both TREC and the MBSR sessions will also be audio-recorded and reviewed. Checklists outlining the essential components of each condition will be used. After completion of the interventions, two raters will conduct tape ratings for fidelity analyses. Approximately 20% of the tapes from each intervention (TREC, MBSR) will be rated. Prior to tape rating, the two raters, who will be blind to study objectives, will receive training in fidelity analysis. Following training, inter-rater reliability will be established by having the two raters rate an initial sample of approximately 10 tapes. A second calibration sample of 5 tapes will then be conducted to focus additional training efforts on items where reliability is inadequate. A third calibration sample of 5 tapes will be conducted midway through the tape rating phase to ensure raters maintain high levels of reliability.

Strategies used to Minimize Study Attrition.

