The research staff will also be using REDcap, a free, secure VA Web application that allows for the collection and entry of research data. In addition to enabling users to develop surveys and databases without additional software, REDcap helps researchers enter, store and manage project data. All data entries will have a study code number but no identifying information. Registration records including the signed consent form will be stored separately from these study records.

[name] will be responsible for reporting adverse events and protocol deviations either personally observed, reported by research staff, or reported by research volunteers. Research staff will inform [name] of adverse events or protocol deviations as soon as reasonably possible after occurrence. [name] will be responsible for the documentation of adverse events and protocol deviations for both annual review and individual events or deviations with decision making guided by the HRPP Standard Operating Procedures for Reporting Research Events and Problems. Unanticipated problems involving risks to subjects or others will be reported to the ACOS for Research and the HSS as soon as possible and no later than three business days after knowledge of the problem. All research staff members will be informed of adverse events or protocol deviations. If protocol changes are required, the [name] will submit modifications to the protocol and consent forms to the HSS as needed, and protocol changes will not be implemented prior to HSS approval unless necessary to avoid hazard to a participant, which is not expected in this minimal risk study.

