If a research volunteer discloses suicidal or homicidal ideation or intent through study questionnaires or direct report to any research staff or investigators, the staff will immediately notify [name] who will determine the appropriate course of response to minimize harm to the volunteer or others. Research staff will remain with the volunteer until [name] takes necessary action. This protocol presents minimal risks to the subjects and adverse events or other problems are not anticipated. In the unlikely event that such events occur, serious and unanticipated and related adverse events or unanticipated problems involving risks to subjects or others will be reported in writing within 48 hours to any appropriate funding and regulatory agencies. VA HSS will be informed of adverse events as described above. The investigator will apprise fellow investigators and study personnel of all adverse events that occur during the conduct of this research project through weekly laboratory meetings and via email.

In Case of Acute Clinical Distress

None of the measures in the study specifically asks about current suicidal or homicidal ideation; however, it is possible that subjects may disclose such ideation either spontaneously or during the screening interview. If a volunteer reports suicidal or homicidal ideation or any intent to harm oneself or another person, we will complete the following procedures. Research staff will inform [name] about the participant's statements. [name] will conduct further questioning on the nature of the ideation or intent, consider the participant's statements, identify risk and protective factors for suicide or homicide, and possibly perform further clinical assessments (e.g., Beck Hopelessness Scale) to best inform clinical decision making. [name] will determine if there is imminent risk to self or other based on these factors.

Should this be the case, she will explain the need to break confidentiality and encourage the subject to voluntarily go with her to the VACHS Psychiatric Emergency Room (PER). If the individual refuses to voluntarily go to the PER, [name] will call [name] VA Police to escort the subject to the PER. The veteran will be encouraged to seek psychiatric services and resources will be provided as appropriate. The procedures will be documented in a VA CPRS Research note. A follow-up phone call will be made with the research volunteer on the following day.

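### No adverse-event question is scheduled during the eight weeks of group treatment or at 3 months, so harms of MBSR and TREC may be under-counted and possibly found unequally in the two arms

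*Combined protocol and SAP*

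**What the plan says.** The Data Safety and Monitoring Plan names the sources of adverse events: one person "will be responsible for reporting adverse events and protocol deviations either personally observed, reported by research staff, or reported by research volunteers". It calls the study minimal risk and adds that "adverse events or other problems are not anticipated". Documentation is to follow the institution's standard operating procedures for reporting, which are not part of the documents.

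Active enquiry is planned around the laboratory session at the end of treatment. At debriefing the experimenter is to "assess any distress that the participants may have experienced". Participants are then told that "they will be contacted between 48-72 hours and then again one-week after their participation to follow-up about any negative reactions they may have had", and the sentence goes on to limit this to that part of the session. Both steps apply to both arms.

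During treatment, under Interim Assessments, "at two time points (weeks 3 and 6 of therapy), participants will be asked to complete the STAXI-2, the BPAG, the FFMQ", then the PCL-5 and two alcohol scales. Table 1 and the descriptions of the post-treatment and follow-up batteries list no adverse-event item. The section on acute clinical distress says that no study measure specifically asks about suicidal or homicidal thoughts.

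Under Study Conditions, the full TREC course is used, "which consists of 8, one-hour weekly sessions", while "MBSR consists of 8, two-hour weekly sessions and will be delivered in group format".

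**The concern.** An event that occurs because of, or during, eight weeks of MBSR or TREC reaches the record only if someone notices it or the participant raises it. The same is true between the one-week contact and the 3-month visit. A low count could then mean few harms or few questions, and the data would not separate the two.

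Unsolicited reporting also depends on opportunity. The experimental arm spends twice as many hours with a group leader as the control arm, and the two courses are described with separate leaders and no common question. Equal true rates could give unequal counts.

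Under Sample Size and Power Considerations, the pilot's main purpose is to inform a larger trial. Whether veterans selected for PTSD and raised trait anger tolerate MBSR is part of what planners of that trial would want to know.

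**Working it through.** The documents give no adverse-event rate, harm analysis or contact-time ratio, so there is no stated figure to reproduce. The check has two parts: what is asked and when, and how far contact time could distort the counts.

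**What is asked and when (same in both arms)**

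| Period | Planned contact | Enquiry about harm |
|---|---|---|
| Group treatment | 8 weekly sessions; questionnaires at weeks 3 and 6; contact after a missed session | None stated |
| Post-treatment session | Questionnaires, script imagery, shock task, debriefing | Distress and harm, focused on the laboratory procedures |
| 48-72 hours and one week later | Two contacts | Reactions to that part of the session |
| From then to 3 months | None stated | None |
| 3-month visit | Questionnaires | None stated |

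The post-treatment session is scheduled once participants have completed their course. Someone who stops early may not reach even the debriefing.

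**Contact time**

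Inputs from Study Conditions: 8 sessions of 2 h (MBSR) and 8 sessions of 1 h (TREC).

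- Group hours: 8 × 2 = 16 h against 8 × 1 = 8 h; ratio 16/8 = 2.0.
- Number of sessions: 8/8 = 1.0.
- With h hours of equal research contact added to each arm, the ratio is (16 + h)/(8 + h). The documents do not give h. At h = 2 it is 18/10 = 1.80; at h = 10 it is 26/18 = 1.44.

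**Illustration of recorded counts under equal true risk**

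Assumptions, none from the documents: 30 participants per arm (60 in total is stated, the split is not), a true risk of 20% in each arm, hence 30 × 0.20 = 6 true events per arm, and a detection probability of 1 − exp(−λ × group hours).

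| λ per hour | Detected, MBSR | Detected, TREC | Ratio | Expected count, MBSR vs TREC (6 true in each) |
|---|---|---|---|---|
| 0.02 | 27% | 15% | 1.85 | 1.6 vs 0.9 |
| 0.05 | 55% | 33% | 1.67 | 3.3 vs 2.0 |
| 0.1 | 80% | 55% | 1.45 | 4.8 vs 3.3 |
| 0.2 | 96% | 80% | 1.20 | 5.8 vs 4.8 |
| 0.5 | 100% | 98% | 1.02 | 6.0 vs 5.9 |

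At the lowest rate, about 1.6 + 0.9 = 2.5 of 12 events are recorded. The loss in both arms is then at least as important as the imbalance. As detection improves, both problems fade.

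**Direction**

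The table assumes the same readiness to disclose per hour in both arms. If reporting is proportional to hours and TREC participants disclose k times as readily per hour, the ratio is 16/(8k) = 2/k. It is 1.0 at k = 2 and below 1 for larger k. The documents give no value for k.

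**After the fix**

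Four scheduled asking occasions in each arm: 4/4 = 1.0, whatever the session length.

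**The case against.** The best defence is that harm is asked about. Debriefing requires the experimenter to assess distress and harm, and two further contacts follow, in both arms. That stands, and it rules out any reading that the plan never enquires. It does not close the gap, because these enquiries are tied to the laboratory session and not to eight weeks of group treatment.

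A reader might infer that MBSR's counts are inflated 2:1. The documents do not support that. Numbers of sessions and research visits are equal, and 2:1 needs strict proportionality to group hours. The direction is open too: TREC includes discussion of current problems, which may prompt disclosure, while much of MBSR is meditation and yoga. Longer MBSR sessions are also more exposure, so extra events there need not be artefact.

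Participants who miss sessions are to be contacted promptly, and collateral contacts are recorded. These are usable routes, but they are retention steps with no stated harm question. The listed sources could include an answer to a question, and the unseen operating procedures might add one. However, those procedures are described as guiding reporting, and nothing in the assessment schedule provides the question.

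It can also be said that the models for STAXI-2 and BPAQ would show an average worsening, since no one-sided test is specified. That is right for means. It does not show how many individuals deteriorated.

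Finally, a reader might see a contradiction between not expecting adverse events and planning for distress. There is none: the plan provides for events that it considers unlikely.

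**Conclusion.** The point holds in a limited form. For the treatment period, and from the one-week contact to 3 months, adverse events are captured only if observed or volunteered, so harms of MBSR and TREC may be under-counted. Unequal detection is a possibility and not a demonstrated bias. With equal true risk and equal disclosure per session or per hour, the spurious MBSR/TREC ratio runs from 1.0 to about 2; with unequal disclosure it could fall below 1. The detection rates, the true risk and the 30 per arm used above are assumptions.

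A reader might conclude that a planned safety comparison is invalid. Data Analyses and Sample Size and Power Considerations contain no comparison of adverse events between arms, so no planned test is affected, and the efficacy analyses are untouched. The consequence is for descriptive safety reporting: a low count could not be told apart from not having asked, and the pilot could say little about tolerability for the larger trial. The case for change rests mainly on its low cost.

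**What to change.** Ask every participant in both arms the same short open adverse-event question at the four assessments that already follow baseline: week 3, week 6, post-treatment and 3 months. Include those who have stopped attending group, where they can be reached. Record each event as solicited or volunteered, and report solicited events descriptively by arm.

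From data already collected, tabulate by arm the number of participants who worsened from baseline on PCL-5, STAXI-2 and BPAQ at each later assessment. State in advance which STAXI-2 score is used and what counts as worsening.

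The cost is a minor amendment: one added form item at four existing assessments and one extra table. The downside is a higher recorded count of minor events, which the solicited/volunteered label lets readers interpret.
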